5.1 Subject Registration (WCM only)

Subjects will be registered within the WRG-CT as per the standard operating procedure for Subject Registration.

6. Study Procedures

6.1 Schedule of Assessments

See Table 1. Schedule of trial events.

Table 1. Schedule of trial events

	Screening (within 48 hours of treatment initiation)	Randomization	Treatment					30 days post- treatment (+/- 2 days)	60 days post- treatment (+/- 2 days)	Follow-Up
			Day 1	Day 7	Day 14	Day 21	Day 28			
Treatment ⁶			X----->							
Informed Consent	X									
Randomization		X								
Demographics	X									
Medical History ¹	X									
Treatment Initiation			X							
Vital Signs ²	X		X	X	X	X	X	X	X	X
CBC w/ diff, platelets	X		X	X	X	X	X	X	X	X
PT, aPTT	X		X	X	X	X	X	X	X	X
D-Dimer	X		X	X	X	X	X	X	X	X
Fibrinogen	X		X	X	X	X	X	X	X	X
Serum Chemistry ³	X		X	X	X	X	X	X	X	X
FVIII/VWF ⁴		X					X		X	X
Activated Protein C Resistance		X					X		X	X
Lupus Anticoagulant aPTT lupus insensitive		X							X	X
Anticardiolipin		X							X	X
Anti-B2 Glycoprotein-1		X							X	X
Correlative Samples ⁵		X							X	X
Vital Status								X	X	X
Adverse Event Evaluation	X	X	X----->							
Concomitant Medications	X	X	X----->							

1. Including information on symptoms of VTE, site and confirmatory tests, arterial thrombosis or microvascular thrombosis, type of anticoagulant/antiplatelet treatment and other treatment.

2. Body weight, blood pressure, heart rate, O2 saturation, mechanical ventilation, Bi-PAP, high flow O2, 100% non-rebreather mask (as applicable).

3. Albumin, alkaline phosphatase, total bilirubin, bicarbonate, BUN, calcium, chloride, creatinine, glucose, LDH, potassium, total protein, SGOT [AST], SGPT [ALT], sodium

4. VWF (von Willebrand Factor)

5. Two 3mL blue sodium citrate tubes. Randomization sample will be drawn prior to initiation of study treatment.

6. Treatment will be given every day for Day 1-Day 28; see section 7.7 for specific dosing schedules.

6.1.1 Screening and Randomization

6.1.1.1 Screening (within 48 hours of treatment initiation)

- Informed Consent
- Medical history, including information on symptoms of VTE, site and confirmatory tests, arterial thrombosis or microvascular thrombosis, type of anticoagulant/antiplatelet treatment and other treatment.
- Demographics
- Vital Signs (body weight, blood pressure, heart rate, O₂ saturation, mechanical ventilation, Bi-PAP, high flow O₂, 100% non-rebreather mask [as applicable])
- Labwork (results must be available prior to enrollment and randomization)
 - CBC w/ diff, platelets
 - PT, PTT
 - D-dimer
 - Fibrinogen
 - Serum Chemistry (albumin, alkaline phosphatase, total bilirubin, bicarbonate, BUN, calcium, chloride, creatinine, glucose, LDH, potassium, total protein, SGOT [AST], SGPT [ALT], sodium)
- Adverse Event Evaluation
- Concomitant Medications

6.1.1.2 Randomization (prior to treatment initiation)

- Randomization
- Labwork (results not required for randomization)
 - FVIII, VWF
 - Activated Protein C Resistance
 - Lupus Anticoagulant
 - aPTT lupus insensitive
 - Anticardiolipin
 - Anti-B2 Glycoprotein-1
 - Two 3 mL blue sodium citrate tubes of plasma for correlative studies
- Adverse Event Evaluation
- Concomitant Medications

6.1.2 Treatment Phase

Eligible subjects will be randomly assigned to Intermediate Prophylaxis Dose or Therapeutic Anticoagulation treatment groups in a 1:1 ratio. Treatment will continue for 28 days continuously.

6.1.2.1 Visit 1 (Day 1)

- Treatment initiation

- Vital Signs (body weight, blood pressure, heart rate, O2 saturation, mechanical ventilation, Bi-PAP, high flow O2, 100% non-rebreather mask [as applicable])
- Labwork
 - CBC w/ diff, platelets
 - PT, PTT
 - D-dimer
 - Fibrinogen
 - Serum Chemistry (albumin, alkaline phosphatase, total bilirubin, bicarbonate, BUN, calcium, chloride, creatinine, glucose, LDH, potassium, total protein, SGOT [AST], SGPT [ALT], sodium)
 - FVIII, VWF
- Activated Protein C Resistance Adverse Event Evaluation
- Concomitant Medications

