2.4.3 Assessment of Potential Risks and Benefits

Hospitalized patients typically receive standard-dose prophylactic anticoagulation to prevent the risk of developing thrombosis throughout their admission. From

April 5, 2020 patients who have required ICU-level care for treatment of COVID-19 in our hospital have been receiving intermediate dose prophylactic anticoagulation due to the observation of higher thrombosis risk noted in critically ill COVID-19 infected patients. Therapeutic dose anticoagulation may be warranted providing that the benefits outweigh the bleeding risk. We hope that this study will provide evidence that higher dose (therapeutic) anticoagulation is more efficacious and as safe as intermediate dose prophylaxis for prevention of thrombosis in critically ill patients with COVID-19 infection.

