2.5 Correlative Studies Background

Additional blood will be collected for correlative studies to further assess the pathophysiology of thrombosis in these patients including: thrombin generation assay, plasmin generation, platelet activation assay, clot lysis time, annexin2.

3. Study Design

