6.1.2.2 Visits 2 through 5 (Day 7, Day 14, Day 21, Day 28)

- Vital Signs (body weight, blood pressure, heart rate, O2 saturation, mechanical ventilation, Bi-PAP, high flow O2, 100% non-rebreather mask [as applicable])
- Labwork
 - CBC w/ diff, platelets
 - PT, PTT
 - D-dimer
 - Fibrinogen
 - Serum Chemistry (albumin, alkaline phosphatase, total bilirubin, bicarbonate, BUN, calcium, chloride, creatinine, glucose, LDH, potassium, total protein, SGOT [AST], SGPT [ALT], sodium)
- Adverse Event Evaluation
- Concomitant Medications

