8.2 Participant Discontinuation/Withdrawal from the Study

Participants are free to withdraw from participation in the study at any time upon request. An investigator may discontinue or withdraw a participant from the study for the following reasons:

- Pregnancy
- Significant study intervention non-compliance
- If any clinical adverse event (AE), laboratory abnormality, or other medical condition or situation occurs such that continued participation in the study would not be in the best interest of the participant
- Disease progression which requires discontinuation of the study intervention
- If the participant meets an exclusion criterion (either newly developed or not previously recognized) that precludes further study participation

- Participant lost to follow-up after several attempts to contact subject to schedule study visit.

The reason for participant discontinuation or withdrawal from the study will be recorded on the Case Report Form (CRF). Subjects who sign the informed consent form and are randomized but do not receive the study intervention may be replaced. Subjects who sign the informed consent form, and are randomized and receive the study intervention, and subsequently withdraw, or are withdrawn or discontinued from the study, will not be replaced.

9. Correlative/Special Studies

For subjects who agree to participate in a research repository, we will collect 5mL of plasma for thrombin generation assays and clot lysis at certain time points (see Section 6.1 for more details). Samples will be stored in a special freezer located in [name] laboratory.

10. Measurement of Effect

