10.4 Other Response Parameters

Normalization of laboratory values including: D-dimer, prothrombin time (PT), fibrinogen, FVIII and VWF and complete blood count

11. Data Reporting / Regulatory Considerations

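### Table 1 and the visit text disagree on whether FVIII, VWF and APC resistance are drawn at Day 1 or at Day 28; under the visit text there is no end-of-treatment value

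*Combined protocol and SAP*

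**What the plan says.** Table 1 (Section 6.1) has a row for FVIII/VWF and a row labelled "Activated Protein C Resistance". Both are marked at randomization, Day 28, 60 days post-treatment and follow-up. Neither is marked at Day 1.

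The visit descriptions give a different set:

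- Section 6.1.1.2 (randomization, before treatment starts) lists FVIII, VWF and APC resistance, in agreement with Table 1.
- Section 6.1.2.1 (Day 1) lists FVIII and VWF under labwork, followed by the line "Activated Protein C Resistance Adverse Event Evaluation". That line looks like two bullets run together, and nothing here depends on the merger.
- Section 6.1.2.2, which covers Days 7, 14, 21 and 28 with one common list, contains none of the three assays.
- Sections 6.1.3.2 (60 days) and 6.1.3.3 (6 months) list all three, in agreement with Table 1.

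Section 10.4 gives a use for two of them. Its further response parameters are "Normalization of laboratory values including: D-dimer, prothrombin time (PT), fibrinogen, FVIII and VWF and complete blood count". It sets no time point and does not name APC resistance.

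**The concern.** Staff cannot follow both sources. Whichever one they use, they omit a draw that the other requires and take one that the other does not contain. The two errors are not equally costly. An extra Day 1 draw falls next to a baseline already taken at randomization and adds little. A missing Day 28 draw removes the only FVIII and VWF value at the end of the 28 treatment days. The arms could then not be compared on these two factors at that point, and a stored schedule error cannot be repaired after the visit has passed. If different staff work from different sources, Day 28 values would be missing according to local practice.

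**Working it through.** The plan gives no figure to reproduce. The check sets the two schedules side by side. The alignment of the Table 1 columns was confirmed on two other rows: vital signs, blank only at randomization, and vital status, marked only in the last three columns.

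| Time point | Table 1: FVIII/VWF, APC resistance | Visit text: FVIII, VWF, APC resistance |
|---|---|---|
| Randomization | yes | yes (6.1.1.2) |
| Day 1 | no | **yes** (6.1.2.1) |
| Days 7, 14, 21 | no | no (6.1.2.2) |
| Day 28 | **yes** | no (6.1.2.2) |
| 30 days post-treatment | no | no (6.1.3.1) |
| 60 days post-treatment | yes | yes (6.1.3.2) |
| 6 months / follow-up | yes | yes (6.1.3.3) |
| Total draws | 4 | 4 |

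**Draws on treatment after Day 1.** One under Table 1 (Day 28), none under the visit text.

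**Spacing of the first two values under the visit text.** Screening falls within 48 hours of treatment initiation, and randomization comes between the two. The randomization and Day 1 samples are therefore at most about 48 hours apart.

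**First value after Day 1 under the visit text.** Treatment runs to Day 28 and the next listed draw is 60 days post-treatment: 28 + 60 = Day 88. With the ±2-day window in Table 1, that is Day 86 to Day 90. This assumes a full 28-day course and that post-treatment is counted from Day 28. Under Table 1 the first value after baseline is at Day 28, which is 88 − 28 = 60 days sooner.

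**Upper limit on what is lost.** One Day 28 sample per participant, so at most 186 across the trial (93 per arm). Deaths and missed visits before Day 28 would lower this.

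**Other parameters in Section 10.4.** D-dimer, PT, fibrinogen and blood count are listed on Days 1, 7, 14, 21 and 28 in both sources. They have four on-treatment values after Day 1 and are not affected.

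**The case against.** The strongest reply is that little rests on these assays. Section 10.4 gives no time point for normalization, and both schedules have FVIII and VWF at baseline, 60 days and 6 months, so normalization by follow-up can be assessed either way. No analysis in Section 12 uses them. Section 3.4 defines study completion by the Schedule of Assessments, which gives Table 1 some standing over the visit lists. It is also not known that anyone would work from the visit text. All of this stands and limits the size of the point. It does not remove the conflict: the visit lists are what staff are likely to consult on the day, and no rule says which source prevails.

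A reader might go further and infer that the biomarker draws cannot show change on treatment at all. The documents do not support that. Under Table 1, randomization against Day 28 is an on-treatment comparison for all three assays, and the remaining Section 10.4 parameters are measured weekly in both sources.

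A reader might also count the correlative tubes as part of the same fault, since they are drawn only at randomization, 60 days and 6 months. There the table and the visit text agree. The purpose in Section 2.5 is to study the pathophysiology of thrombosis, and no objective promises an on-treatment comparison of the arms. That is a consistent design choice.

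**Conclusion.** The inconsistency is real and is wrong as written. The two sources agree on three of four draws and conflict on the fourth, Day 1 against Day 28. If the visit text is followed, end-of-treatment FVIII, VWF and APC resistance are lost, and the first value after Day 1 moves to about Day 88 after a full course. The effect is limited to one additional response parameter. Thirty-day mortality, length of ICU stay, the thrombosis composite and the bleeding outcomes are unaffected.

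The conclusion rests only on reading the schedule against the visit lists. It assumes nothing about how many staff follow either source. It should not be stretched to a claim that pre-study heparin distorts the baseline assays: the documents say nothing about such interference, and they do provide for recording of drug administration (Section 7.3) and for anti-Xa checks to guide dosing (Sections 3.1 and 7.7).

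**What to change.** Reconcile Sections 6.1.2.1 and 6.1.2.2 with Table 1 and state which source prevails if they differ. The documents do not say which was intended, so the sponsor must confirm it. Since a pre-treatment baseline is already drawn at randomization, the version that keeps an end-of-treatment value is to list FVIII, VWF and APC resistance at Day 28 in Section 6.1.2.2 and remove them from Day 1 in Section 6.1.2.1. Section 10.4 could also state when normalization is judged.

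The cost is amendment wording. The number of draws stays at four, and blood is already taken at Day 28 for other tests, so no visit is added. If enrollment has begun, tabulate by arm which participants have a Day 1 value, a Day 28 value or both, so that any gap is reported as a schedule conflict.

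As an optional suggestion only, the same amendment could consider adding the correlative tubes to one venepuncture already scheduled on treatment.

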6.1.2.2 Visits 2 through 5 (Day 7, Day 14, Day 21, Day 28)

- Vital Signs (body weight, blood pressure, heart rate, O2 saturation, mechanical ventilation, Bi-PAP, high flow O2, 100% non-rebreather mask [as applicable])
- Labwork
 - CBC w/ diff, platelets
 - PT, PTT
 - D-dimer
 - Fibrinogen
 - Serum Chemistry (albumin, alkaline phosphatase, total bilirubin, bicarbonate, BUN, calcium, chloride, creatinine, glucose, LDH, potassium, total protein, SGOT [AST], SGPT [ALT], sodium)
- Adverse Event Evaluation
- Concomitant Medications

6.1.3 Follow-up Phase

Following completion of treatment, subjects will enter a 6-month follow-up period.

6.1.3.1 Visit 6 (30 Days Post-Treatment)

- Vital Signs (body weight, blood pressure, heart rate, O2 saturation, mechanical ventilation, Bi-PAP, high flow O2, 100% non-rebreather mask [as applicable])
- Labwork
 - CBC w/ diff, platelets
 - PT, PTT
 - D-dimer
 - Fibrinogen
 - Serum Chemistry (albumin, alkaline phosphatase, total bilirubin, bicarbonate, BUN, calcium, chloride, creatinine, glucose, LDH, potassium, total protein, SGOT [AST], SGPT [ALT], sodium)
- Adverse Event Evaluation

- Concomitant Medications
- Vital Status

6.1.3.2 Visit 7 (60 Days Post-Treatment)

- Vital Signs (body weight, blood pressure, heart rate, O2 saturation, mechanical ventilation, Bi-PAP, high flow O2, 100% non-rebreather mask [as applicable])
- Labwork
 - CBC w/ diff, platelets
 - PT, aPTT
 - D-dimer
 - Fibrinogen
 - Serum Chemistry (albumin, alkaline phosphatase, total bilirubin, bicarbonate, BUN, calcium, chloride, creatinine, glucose, LDH, potassium, total protein, SGOT [AST], SGPT [ALT], sodium)
 - FVIII, VWF
 - Activated Protein C Resistance
 - Lupus Anticoagulant
 - aPTT lupus insensitive
 - Anticardiolipin
 - Anti-B2 Glycoprotein-1
 - Two 3 mL blue sodium citrate tubes of plasma for correlative studies
- Adverse Event Evaluation
- Concomitant Medications
- Vital Status

6.1.3.3 Visit 8 (6 Months Post-Treatment)

- Vital Signs (body weight, blood pressure, heart rate, O2 saturation, mechanical ventilation, Bi-PAP, high flow O2, 100% non-rebreather mask [as applicable])
- Labwork
 - CBC w/ diff, platelets
 - PT, PTT
 - D-dimer
 - Fibrinogen
 - Serum Chemistry (albumin, alkaline phosphatase, total bilirubin, bicarbonate, BUN, calcium, chloride, creatinine, glucose, LDH, potassium, total protein, SGOT [AST], SGPT [ALT], sodium)
 - FVIII, VWF
 - Activated Protein C Resistance
 - Lupus Anticoagulant
 - aPTT lupus insensitive
 - Anticardiolipin
 - Anti-B2 Glycoprotein-1
 - Two 3 mL blue sodium citrate tubes of plasma for correlative studies
- Adverse Event Evaluation
- Concomitant Medications

- Vital Status

7. Study Intervention

7.1 Study Intervention Description

Lovenox® (Enoxaparin sodium) is an anticoagulant medication approved by the FDA for the prophylaxis and treatment of deep vein thrombosis and pulmonary embolism. Enoxaparin is available as an injectable and is delivered subcutaneously. Enoxaparin is contraindicated in patients with active major bleeding and a history of immune-mediated heparin-induced thrombocytopenia (HIT) within the past 100 days or in the presence of circulating antibodies.

Heparin sodium (unfractionated heparin) is an anticoagulant indicated for the prophylaxis and treatment of venous thromboembolism and pulmonary embolism. The use of unfractionated heparin is contraindicated in patients with a history of heparin-induced thrombocytopenia, patients in an uncontrolled bleeding state except when due to disseminated intravascular coagulation, and in patients who cannot have suitable blood coagulation tests performed at appropriate intervals.

Argatroban is a synthetic direct thrombin inhibitor that is approved for the prophylaxis or treatment of thrombosis in adult patients with heparin-induced thrombocytopenia (HIT). Argatroban is contraindicated in patients with major bleeding.

Fondaparinux (Arixtra®) is a synthetic and specific inhibitor of Factor X (Xa) indicated for the prophylaxis and treatment of deep vein thrombosis or acute pulmonary embolism. It is supplied as a sterile, preservative-free injectable solution for subcutaneous use.

7.2 Availability

All drugs described in this protocol are FDA approved for the intended indications and can be obtained through a prescription.

7.3 Acquisition and Accountability

All drugs administered while subjects are hospitalized will be documented in the electronic medical records system. Any drugs taken at home by the subject will be documented in a study-specific drug diary and reviewed with the subject's treating physician at their next clinic visit.

7.4 Formulation, Appearance, Packaging, and Labeling

Lovenox® (Enoxaparin) is a sterile aqueous solution containing enoxaparin sodium, a low molecular weight heparin. The pH of the injection is 5.5 to 7.5. Lovenox® is a clear, colorless to pale yellow sterile solution that may be administered by intravenous or subcutaneous injection only. Lovenox® is manufactured by Sanofi.

Heparin sodium (unfractionated heparin) is available in 0.45% Sodium Chloride Injection and 5% Dextrose Injection.

Argatroban Injection in 0.9% sodium chloride is a clear, colorless to pale yellow solution. It is supplied as a single use vial containing 125 mg argatroban in 125 mL of aqueous sodium chloride solution (1 mg/mL). Argatroban Injection is manufactured by Sandoz, Inc.

Arixtra® (fondaparinux sodium) is supplied as a sterile, preservative-free injectable solution for subcutaneous use. Each single dose, prefilled syringe, affixed with an automatic needle protection system, contains 2.5 mg of fondaparinux sodium in 0.5 mL, 5.0 mg of fondaparinux sodium in 0.4 mL, 7.5 mg of fondaparinux sodium in 0.6 mL or 10.0 mg of fondaparinux sodium in 0.8 mL of an isotonic solution of sodium chloride and water for injection. The final drug product is a clear and colorless to slightly yellow liquid with a pH between 5.0 and 8.0. Arixtra® is manufactured by GlaxoSmithKline.

7.5 Product Storage and Stability

Lovenox® should be stored at 25°C with excursions permitted to 15°C-30°C (59°F-86°F). Do not store multiple-dose vials for more than 28 days after the first use.

Heparin sodium should be stored at 20°C to 25°C (68°F-77°F). Avoid excessive heat. Do not freeze.

Argatroban vials should be stored in their original cartons at 20°-25° C (68°-77°F). The product should be retained in the original carton to protect from light. Do not freeze.

Arixtra® (fondaparinux sodium) should be stored at 25°C (77°F), with excursions permitted to 15-30°C (59-86°F).

7.6 Preparation

See Appendix A for package inserts of each drug used in this protocol.

7.7 Dosing and Administration

All subjects will be dosed continuously for 28 days. Specific dosing instructions per drug and per arm are as follows:

Intermediate Dose Prophylaxis arm:

Subjects randomized to the Intermediate Dose Prophylaxis arm will receive one of the following treatments:

- If CrCl \geq 30 ml/min, Enoxaparin 0.5 mg/kg subcutaneously every 12 hours
- If CrCl less than 30 ml/min, Enoxaparin 0.5 mg/kg subcutaneously every 24 hours
- If patient develops acute kidney injury (defined by KDIGO guidelines): unfractionated heparin 7,5000 units subcutaneously every 8 hours.
- If patient has history of HIT, fondaparinux 2.5 mg daily subcutaneously

For subjects receiving Enoxaparin, adjust dose based on anti-Xa activity 4 hours after the 3rd dose; goal of 0.4 – 0.6 IU/mL.

Therapeutic Anticoagulation arm:

Full dose parenteral anticoagulation per institutional protocol:

- Enoxaparin 1 mg/kg subcutaneously every 12 hours if CrCl \geq 30mL/min.
- Enoxaparin 1 mg/kg subcutaneously daily if CrCl <30 mL/min.
- If AKI develops, Unfractionated heparin (UFH) to target anti-Xa level 0.3 – 0.7 IU/mL or aPTT (according to institutional protocol).
- Argatroban (if heparin-induced thrombocytopenia [HIT] and CrCl <50 ml/min), dosed according to institutional protocol.
- Fondaparinux (if HIT and CrCl \geq 50 ml/min), dosed according to patient weight:
 - \geq 100 kg: 10 mg daily
 - <100 kg but \geq 50 kg: 7.5 mg daily
 - <50 kg: 5 mg daily

Therapeutic dose adjusted per NYP Infonet protocols.

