2.2 Investigational Agent

All of the drugs described in this protocol are FDA approved for the intended indications and can be obtained through a prescription.

Enoxaparin (Lovenox®) is an anticoagulant medication approved by the FDA for the prophylaxis and treatment of deep vein thrombosis and pulmonary embolism. Enoxaparin is available as an injectable and is delivered subcutaneously. For this study, subjects randomized to the intermediate dose prophylaxis arm will receive Enoxaparin 0.5 mg/kg subcutaneously every 12 hours if their creatinine clearance is \geq 30 ml/min. Subjects with creatinine clearance of < 30 ml/min will receive Enoxaparin 0.5 mg/kg subcutaneously every 24 hours. Subjects randomized to the therapeutic anticoagulation arm will receive Enoxaparin 1 mg/kg subcutaneously every 12 hours if their creatinine clearance is \geq 30 ml/min and 1 mg/kg subcutaneously every 24 hours if creatinine clearance of < 30 ml/min.

Heparin sodium (unfractionated heparin) is an anticoagulant indicated for the prophylaxis and treatment of venous thromboembolism. For this study, subjects on the intermediate dose prophylaxis arm who develop acute kidney injury, as defined by the KDIGO guidelines, may receive unfractionated heparin 7,500 units subcutaneously every 8 hours. Subjects on the therapeutic anticoagulation arm may receive unfractionated heparin intravenous continuous infusion to target anti-Xa level of 0.3 – 0.7 IU/mL or therapeutic range aPTT, according to institutional guidelines.

Argatroban is a synthetic direct thrombin inhibitor that is approved for the prophylaxis and treatment of thrombosis in adult patients with heparin-induced thrombocytopenia (HIT). Subjects randomized to the therapeutic anticoagulation arm with a history of HIT may receive argatroban dosed according to institutional protocol.

Fondaparinux (Arixtra®) is a synthetic and specific inhibitor of Factor X (Xa) indicated for the prophylaxis and treatment of deep vein thrombosis or acute pulmonary embolism. Subjects randomized to the intermediate dose prophylaxis arm with a history of HIT will receive fondaparinux 2.5 daily subcutaneously. Subjects randomized to the therapeutic anticoagulation arm with a history of HIT and creatinine clearance of \geq 50 ml/min may receive fondaparinux dosed according to weight: if \geq 100 kg, 10 mg daily subcutaneously; if < 100 kg but \geq 50 kg, 7.5 mg daily subcutaneously; if < 50 kg, 5 mg daily subcutaneously.

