3.1 Overall Design

Prospective phase IV, open-label randomized control trial comparing two different doses of parenteral anticoagulation (Intermediate vs. therapeutic dose) in critically ill patients with COVID-19 infection. The purpose of the study is to determine if therapeutic dose anticoagulation improves 30-day mortality in COVID-19 positive patients compared to intermediate dose prophylaxis. Patients will be randomized 1:1 to either intermediate dose prophylaxis (standard of care arm) or therapeutic-dose anticoagulation (experimental arm). Each arm will enroll 93 patients, for a total of 186 patients. Treatment on both arms will be for 28 days continuously. Patients will enter the study at the time of hospital admission. Patients will be recruited by their treating physician in the hospital or by the principal investigator.

Intermediate dose prophylaxis:

- If CrCl \geq 30 ml/min, Enoxaparin 0.5 mg/kg SC every 12 hours
- If CrCl less than 30 ml/min, Enoxaparin 0.5 mg/kg SC every 24 hours
- If patient develops acute kidney injury (defined by KDIGO guidelines): unfractionated heparin 7,500 units SC every 8 hours
- If patient has a history of HIT, Fondaparinux 2.5 mg daily subcutaneously

For patients receiving Enoxaparin, adjust dose based on anti-Xa activity 4 hours after 3rd dose; goal of 0.4 – 0.6 IU/mL for intermediate prophylactic dose.

Therapeutic anticoagulation:

Full dose parenteral anticoagulation per institutional protocol:

- Enoxaparin 1 mg/kg SC every 12 hours If CrCl equal or more than 30 mL/min to target peak anti-Xa level 4 hours after the 3rd dose; goal 0.6 - 1.0 IU/mL
- Enoxaparin 1 mg/Kg SC every 24 hours If CrCl less than 30 mL/min to target peak anti-Xa level 4 hours after the 3rd dose; goal 0.6 - 1.0 IU/m
- If patient develops acute kidney injury (defined by KDIGO guidelines): Unfractionated heparin (UFH) to target anti-Xa level 0.3 – 0.7 IU/mL or aPTT (according to institutional protocol)

- If patient has a history of HIT or develops HIT:
 - Fondaparinux (if CrCl \geq 50 ml/min).
 - If patient weight is \geq 100 kg, 10 mg daily
 - If patient weight is $<$ 100kg but \geq 50 kg, 7.5 mg daily
 - If patient weight is $<$ 50 kg, 5 mg daily
 - Or Argatroban if CrCl $<$ 50 ml/min), dosed according to institutional protocol.

Therapeutic dose adjusted per NYP Infonet protocols.

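### In the intermediate arm, the dosing lines in 7.7 offer only enoxaparin or unfractionated heparin to a patient who develops heparin-induced thrombocytopenia on study, and 7.1 lists both as contraindicated

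*Combined protocol and SAP*

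**What the plan says.** Section 7.7 states that intermediate-arm subjects "will receive one of the following treatments" and then gives four lines:

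- creatinine clearance (CrCl) of 30 ml/min or more: "Enoxaparin 0.5 mg/kg subcutaneously every 12 hours";
- CrCl below 30: "If CrCl less than 30 ml/min, Enoxaparin 0.5 mg/kg subcutaneously every 24 hours";
- AKI: "If patient develops acute kidney injury (defined by KDIGO guidelines): unfractionated heparin", given subcutaneously;
- past HIT: "If patient has history of HIT, fondaparinux 2.5 mg daily subcutaneously".

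Sections 1, 2.2 and 3.1 also tie intermediate-arm fondaparinux to a history of HIT. For the therapeutic arm, the HIT line in 3.1 opens with "If patient has a history of HIT or develops HIT", and the HIT lines in 7.7 are triggered by HIT without further qualification.

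Section 7.1 lists enoxaparin as contraindicated when there has been immune-mediated HIT in the preceding 100 days or when antibodies are circulating. For heparin it says: "The use of unfractionated heparin is contraindicated in patients with a history of heparin-induced thrombocytopenia".

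On AKI in the intermediate arm, 2.2 is permissive: subjects "who develop acute kidney injury, as defined by the KDIGO guidelines, may receive unfractionated heparin 7,500 units subcutaneously every 8 hours". The corresponding line in 7.7 is not. HIT is not among the exclusion criteria in 4.3.

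**The concern.** Section 7.7 is the operative dosing section, and sites will follow it and build orders from it. Both arms are planned for 28 days of mainly heparin-based treatment, so HIT arising on study is foreseeable. The authors foresaw it for the therapeutic arm. For the intermediate arm, a site that follows the lines as written finds no non-heparin option for such a patient and is left with drugs that the same protocol contraindicates. At stake is the safety of individual patients, not the mortality comparison.

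**Working it through.** There is no figure in the plan to reproduce. The check compares the text of the sections, followed by a rough count.

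**Step 1. Which lines match.** The four intermediate-arm lines in 7.7 were read literally. The two CrCl lines together cover every value, and neither excludes HIT or AKI. The AKI line does not exclude HIT. The fondaparinux line requires a history of HIT. Each row below holds for CrCl below 30 and for CrCl of 30 or more.

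| HIT status | AKI | Lines that match | Non-heparin line? |
|---|---|---|---|
| History | No | Enoxaparin, fondaparinux | Yes |
| History | Yes | Enoxaparin, unfractionated heparin, fondaparinux | Yes |
| Develops on study | No | Enoxaparin | No |
| Develops on study | Yes | Enoxaparin, unfractionated heparin | No |

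Four rows times two CrCl ranges give 8 combinations with HIT. In 2 × 2 = 4 of them, all on-study HIT, no non-heparin line matches. In the other 4, fondaparinux matches alongside at least one heparin product.

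**Step 2. Compare with 7.1.** HIT that arises within the 28 planned treatment days is necessarily less than 100 days old while that treatment runs, so it falls inside the enoxaparin window. The heparin contraindication has no time limit. A remote history without antibodies is outside the enoxaparin contraindication but inside the heparin one.

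**Step 3. The therapeutic arm.** In 7.7 its HIT lines divide at CrCl 50 and together cover every value, so a non-heparin line always matches when HIT is present. Its AKI line, like that of the intermediate arm, is not conditioned on the absence of HIT. The overlap between AKI and HIT therefore exists in both arms, while the missing line for on-study HIT is confined to the intermediate arm.

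**Step 4. AKI and CrCl.** Because the CrCl lines cover everyone, every AKI patient matches an enoxaparin line and the heparin line. Without HIT, the 7.1 HIT contraindications do not come into play; the text simply does not say which line governs. For the intermediate arm, the permissive wording in 2.2 and the unqualified line in 7.7 also differ.

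**Step 5. Size.** The documents give no rate for HIT or AKI, so these are assumed ranges.

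- HIT, past or new, 0.5% to 3%: 0.005 × 93 = 0.5 and 0.03 × 93 = 2.8 intermediate-arm patients. On-study HIT alone is some part of this.
- HIT together with AKI, taking AKI at 20% to 50% and independent of HIT: 0.005 × 0.20 × 93 = 0.1 and 0.03 × 0.50 × 93 = 1.4 patients.

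**The case against.** The strongest reply is that the authors use HIT terms loosely. Section 2.2 speaks of a history of HIT for the therapeutic arm too, and only 3.1 mentions HIT that develops. A patient diagnosed on study could be said to have a history from that day, and 7.1 itself uses that word. On that reading the fondaparinux line would apply, and only the question of precedence would remain. This has some force. Against it, 3.1 treats the two situations as distinct, and uses only the first for the intermediate arm in the same section. A dosing rule should not depend on which reading a site adopts.

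Second, 7.9 allows treatment to stop for unacceptable adverse events or on the investigator's judgment, 8.1 lets the investigator decide on changes in management, and 7.1 is itself protocol text. These provisions lower the practical risk. None of the stopping provisions names HIT or an alternative drug, so the conflict in the text remains.

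Third, a reader might infer that patients with a past history of HIT are also directed to heparin once AKI occurs. The documents do not support that for the intermediate arm. Section 2.2 makes fondaparinux mandatory for a history of HIT and heparin permissive for AKI, and 7.1 contraindicates the heparin. Together these point to one answer; what is missing is a statement of it in 7.7.

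**Conclusion.** The point holds for the intermediate arm: on a literal reading, no non-heparin line in 7.7 covers HIT that develops on study, and the lines that do match conflict with 7.1. This rests on taking the distinction in 3.1 at face value. The overlap of the AKI line with the HIT and CrCl lines is a secondary matter of unstated precedence. The number affected is probably a handful at most, on assumed rates. Sample size, alpha and the primary analysis are untouched.

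Three wider inferences are not supported:

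- A reader might see a contradiction in fondaparinux having a renal limit in the therapeutic arm only. The arms use different fondaparinux doses, and 7.1 states no renal contraindication for it.
- A reader might take 7.7.1 to make creatinine clearance the sole basis for modification. It refers back to 7.7, which contains the AKI line.
- A reader might argue that arm-specific switching rules bias the bleeding or thrombosis comparisons. The two arms handle AKI and low CrCl in parallel, and HIT cases are too few to distort those comparisons materially.

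**What to change.** Reconcile sections 1, 2.2, 3.1, 7.1 and 7.7 so that:

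- the dosing lines do not conflict with the contraindications in 7.1;
- HIT that arises on study is addressed in the intermediate arm;
- it is clear, in each arm, which line governs when several apply;
- 2.2 and 7.7 agree on whether the AKI switch in the intermediate arm is required or optional.

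Which agent, dose and rule should apply is for the sponsor's clinicians. The cost is one amendment to the dosing text, with IRB approval under 11.2.1, and an update of any order sets built on it. It needs no extra patients, visits or tests, and no change to the statistical section.
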